Evaluation of Intraoperative use of Dexycu on the Signs and Symptoms of Dry Eye

Sponsor: **SR Cornea Consultants**
[name]
[name]
Name and title of person(s) authorized to sign the protocol for
the sponsor: [name]

Monitor: **[name]**

Medical Expert: **[name]**

Investigators: **[name]**

Clinical Laboratory(ies): **NA**

Study Product: **DEXYCU (dexamethasone intraocular suspension) 9%**

Protocol Number: **NCT04184999**
April 10, 2019

Table of Contents

Study Summary

- 1. Introduction**
 - 1.1 Background**
 - 1.2 Investigational or Study Product**
 - 1.3 Preclinical Data**
 - 1.4 Clinical Data to Date**
 - 1.5 Dose Rationale**
 - 1.6 Risks/Benefits**
- 2. Study Objectives**
- 3. Study Design**
 - 3.1 General Design**
 - 3.2 Primary/Secondary Study Endpoints**
- 4. Subject Selection and Withdrawal**
 - 4.1 Inclusion Criteria**
 - 4.2 Exclusion Criteria**
 - 4.3 Subject Recruitment and Screening**
 - 4.4 Early Withdrawal of Subjects**
- 5. Investigational Product**
 - 5.1 Description**
 - 5.2 Treatment Regimen**
 - 5.3 Method for Assigning Subjects to Treatment Groups**
 - 5.4 Subject Compliance Monitoring**
 - 5.5 Prior and Concomitant Therapy**
 - 5.6 Packaging, Receiving, Storage, Dispensing and Return**
- 6. Study Procedures**
- 7. Statistical Plan**
 - 7.1 Sample Size Determination**
 - 7.2 Statistical Methods**
 - 7.3 Subject Population(s) for Analysis**
- 8. Safety and Adverse Events**
 - 8.1 Definitions**
 - 8.2 Assessment of Safety and Efficacy**
 - 8.3 Recording and Reporting of Adverse Events**
 - 8.4 Unblinding Procedures**
 - 8.5 Stopping Rules**
 - 8.6 Medical Monitoring**
- 9. Data Handling and Record Keeping**
 - 9.1 Confidentiality**
 - 9.2 Source Documents**
 - 9.3 Records Retention**
- 10. Study Monitoring, Auditing, and Inspecting**
- 11. Ethical Considerations**

STUDY SUMMARY

Title	Evaluation of intraoperative use of Dexycu on the Signs and Symptoms of Dry Eye
Protocol Number	10
Phase	Phase IV
Methodology	Prospective Randomized Controlled Trial
Study Duration	3 weeks
Study Center(s)	Single-Center
Objectives	To evaluate the impact of intraoperative Dexycu during cataract surgery on the signs and symptoms of dry eye
Number of subjects	40
Main Inclusion and Exclusion Criteria	
Inclusion: Patients undergoing bilateral cataract surgery
 
Exclusion: Patients with severe ocular surface disease as defined by central corneal staining with fluorescein and/or a tear film osmolarity of greater than 340 in either eye

Study product, Dose, Route, Regimen	DEXYCU (dexamethasone intraocular suspension) 9%, administered as a single dose, intraocularly in the posterior chamber at the end of surgery. The dose is .005 mL of dexamethasone 9% (equivalent to 517 micrograms)
Duration of subjects participation	Patients scheduled to undergo bilateral cataract surgery will be screened and have dry eye testing. If enrolled in the study, patients will have dry eye testing at 1 week and 3 weeks after surgery.
Reference product	The control group will utilize a standard post-cataract surgery regimen of topical gatifloxacin and topical prednisolone acetate.

1 Introduction

Evaluation of intraoperative use of Dexycu on the Signs and Symptoms of Dry Eye is a clinical research protocol and the study will be conducted in accordance with the protocol, Good Clinical Practice Standards, and applicable regulatory requirements.

1.1 Background

Multiple studies have established the relationship between dry eye and cataract surgery. First, a majority of patients undergoing cataract surgery have dry eye signs including decreased tear break up time (63%) and positive corneal staining (77%). Second, patients experience an increase in dry eye symptoms after cataract surgery compared to baseline. Third, Snellen visual acuity and contrast sensitivity are impacted by dry eye after cataract surgery.

The objective of this clinical research is to evaluate whether the signs and symptoms of dry eye after cataract surgery improve with the addition of a DEXYCU intraocular injection.

1.2 Investigational/Study Product

DEXYCU contains dexamethasone 9% as a sterile suspension for intraocular ophthalmic administration. DEXYCU is provided as a kit for administration of a single dose of 0.005 mL of 9% dexamethasone.

1.3 Preclinical Data

Not applicable.

1.4 Clinical Data to Date

Clinical efficacy was evaluated in a randomized, double masked, placebo controlled trial (NCT2006888) in which subjects received either DEXYCU or placebo (vehicle). A dose of 5 microliters of DEXYCU or vehicle was administered by the physician at the end of the surgical procedure. The primary efficacy endpoint for the study was the proportion of patients with anterior chamber cell clearing on postoperative day 8. The percentage of patients with anterior chamber clearing at Day 8 was 2% in the placebo group, and 57%, and 60% in the 342 and 517 microgram treatment groups.

1.5 Dose Rationale

See section 1.4

1.6 Risk/Benefits

The following adverse events rates are derived from three clinical trials in which 339 patients received the 517 microgram dose of DEXYCU. The most commonly reported adverse reactions occurred in 5-15% of subjects and included increases in intraocular pressure, corneal edema, and iritis. Other ocular adverse reactions occurring in 1-5% of subjects included, corneal endothelial cell loss, blepharitis, eye pain, cystoid macular edema, dry eye, ocular inflammation, posterior capsular opacification, blurred vision, reduced visual acuity, vitreous floaters, foreign body sensation, photophobia, and vitreous detachment.

2 Study Objectives

The objective of this clinical research is to evaluate whether the signs and symptoms of dry eye after cataract surgery improve with the addition of a DEXYCU intraocular injection. Multiple studies have established that dry eye worsens after cataract surgery. There is also

a strong body of evidence that shows that dry eye is inflammatory. The objective of this study is to evaluate whether the intraocular use of steroid impacts dry eye.

3 Study Design

3.1 General Design

- The type/design of the study:
 - Prospective randomized controlled trial
- A description of the measures taken to minimize/avoid bias:
 - Patients undergoing bilateral cataract surgery will be randomized to the DEXYCU group (standard postoperative cataract regimen + intraoperative DEXYCU) in one eye or the STANDARD group (standard postoperative cataract regimen). Randomization will be done after screening visit, prior to surgery on the first eye and will be done by coin flip. Standard cataract regimen to be used: topical prednisolone acetate 1% qid and topical gatifloxacin qid for 1 week, then tid for 1 week, then bid for 1 week.
- Expected duration of subject participation
 - 3 weeks after cataract surgery
 - Patients undergoing cataract surgery will have dry eye testing prior to surgery, 1 week after surgery, and 3 weeks after surgery
- A summary description of the sequence and duration of all trial periods including follow-up, if any
 - Patients undergoing cataract surgery will have dry eye testing prior to surgery, 1 week after surgery, and 3 weeks after surgery

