3.2 Primary/Secondary Endpoints

Primary endpoints:

- 1) Tear film Osmolarity as measured on Tear Lab system
- 2) Corneal Staining (Oxford grading scale 0-15)

Secondary endpoint:

- 3) Satisfaction questionnaire – How satisfied are you with your surgery? (Graded 0-4)

4 Subject Selection and Withdrawal

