4.3 Subject Recruitment and Screening

Subjects will be recruited for the study from principal investigator's clinical practice. As part of the informed consent process, patients will be offered a DEXYCU injection and given a brochure/handout discussing DEXYCU. As part of the standard cataract evaluation process, both tear film osmolarity and corneal staining will be performed.

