5.3 Method for Assigning Subjects to Treatment/Dosing Groups

Patients undergoing bilateral cataract surgery will be randomized to the DEXYCU group (standard postoperative cataract regimen + intraoperative DEXYCU) in one eye or the STANDARD group (standard postoperative cataract regimen). Randomization will be done after screening visit, prior to surgery on the first eye and will be done by coin flip. Patients who are randomly assigned to the DEXYCU group will receive a sequentially numbered drug kit.

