5.6 Packaging, Receiving, Storage, Dispensing and Return

Dexycu will be stored in a locked cabinet. Usage of the medication will be logged.

6 Study Procedures

- Screening Visit
- Day 1 Postoperative Visit
- Day 7 Postoperative Visit
- Day 21 Postoperative Visit

At all visits, visual acuity, eye pressure measurements, tear film osmolarity, and corneal staining will be measured and recorded. At days 7 and 21, patient satisfaction scores will be measured.

7 Statistical Procedures

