8.4 Randomization Codes

Patients undergoing bilateral cataract surgery will be randomized to the DEXYCU group (standard postoperative cataract regimen + intraoperative DEXYCU) in one eye or the STANDARD group (standard postoperative cataract regimen). Randomization will be done after screening visit, prior to surgery on the first eye and will be done by coin flip. Patients who are randomly assigned to the DEXYCU group will receive a sequentially numbered drug kit.

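### The plan lists a coin flip and a shared drop regimen as its only measures against bias; no visible passage masks the patient or the person who grades corneal staining, and none describes a record of the flip

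*Combined protocol and SAP*

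**What the plan says.** Section 3.1 has a bullet for measures that reduce bias. It contains two things: randomization, with its method and timing ("Randomization will be done after screening visit, prior to surgery on the first eye and will be done by coin flip"), and a topical regimen that both groups receive. Sections 5.3 and 8.4 repeat the flip and add: "Patients who are randomly assigned to the DEXYCU group will receive a sequentially numbered drug kit". Section 5.6 adds: "Usage of the medication will be logged".

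The endpoints in section 3.2 are tear film osmolarity and "Corneal Staining (Oxford grading scale 0-15)" as primaries, and a 0-4 satisfaction question as secondary. On timing, section 6 says: "At days 7 and 21, patient satisfaction scores will be measured". Section 4.3 says that, during consent, "patients will be offered a DEXYCU injection and given a brochure/handout discussing DEXYCU".

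The table of contents lists "8.4 Unblinding Procedures", but the section that carries that number in the body is "8.4 Randomization Codes". It restates the flip and says nothing about masking or unblinding.

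**The concern.** The endpoints differ in how far knowledge of the allocation can move them. Osmolarity is a device reading. Staining on a 0-15 scale is a judgement by an observer whom the plan does not name. Satisfaction is a rating by patients who have been told about DEXYCU and given a handout on it. The symptom scores listed in section 9.1 are not named as endpoints, but they are exposed in the same way.

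If the patient or grader learns the allocation, which nothing visible prevents, a group difference in staining or satisfaction may reflect expectation rather than the drug. The analysis in section 7.2 could not separate the two. For one of the two primary endpoints, that weakens the main conclusion.

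A smaller matter is that the visible text describes no record of what the coin showed. Agreement between flip and treatment could not be checked from the records described.

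**Working it through.** **1. Search of the text.** The plan gives no figure on this point to reproduce, so the first step is to set the relevant places side by side.

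- Study Summary and 3.1: a prospective randomized controlled trial, with no masking term attached.
- 1.4: the only masking wording in the document, and it describes an earlier trial.
- Study Summary, reference product: standard drops, with no sham or vehicle injection described.
- 3.2 and section 6: staining is graded, with no statement of who grades or what that person knows.
- 5.3 and 5.6: numbered kits for the DEXYCU group and a usage log. These show who received the drug, not the result of the flip.
- 5.4 and 9.2 (binder tabs) and 9.1 (data collected): no randomization form and no assigned-group field is listed.

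**2. What a lean in grading could do.** The documents give neither a significance level nor an SD. Assumed: two-sided 5%; no true effect; a score treated as continuous; an apparent difference of b SD caused only by knowledge of the allocation, with b = 0.2, 0.3 or 0.5. The sample size of 40 is from section 7.1.

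The allocation wording in 3.1, 5.3 and 8.4 can mean that patients are assigned to groups or that one eye of each patient receives DEXYCU, so both readings are shown.

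- Patients as the unit: a two-group ANOVA F test equals a two-sided t-test. Noncentrality = b × √(n₁n₂/(n₁+n₂)), 38 df, critical value 2.024.
- Fellow-eye pairs, analysed as pairs: SD of the difference = SD × √(2(1−ρ)), so noncentrality = b × √(40/(2(1−ρ))), 39 df, critical value 2.023. The correlation ρ is assumed to be 0 or 0.5.

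The false-positive rate is the probability that a noncentral t variate falls outside the critical values.

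| Comparison | Multiplier of b | b = 0.2 | b = 0.3 | b = 0.5 |
|---|---|---|---|---|
| 20 v 20 patients | √10 = 3.162 | 9.5% | 15.2% | 33.8% |
| 14 v 26 patients | √9.1 = 3.017 | 9.0% | 14.3% | 31.2% |
| 40 pairs, ρ = 0 | √20 = 4.472 | 14.1% | 25.8% | 58.7% |
| 40 pairs, ρ = 0.5 | √40 = 6.325 | 23.5% | 45.7% | 86.9% |

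The 14 v 26 row allows for the uneven split that a coin can produce. The pair rows suit staining. They suit satisfaction only if it is asked for each eye, which section 3.2 does not say. None of the rows applies to osmolarity.

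**3. Whether group totals could replace a log.** With X ~ Binomial(40, 0.5), P(14 ≤ X ≤ 26) = 96.2%. If k results ended up switched towards one side, P(14 ≤ X + k ≤ 26) is 92.0% for k = 2 and 78.5% for k = 4. The totals therefore say little about whether each flip was followed. That is true of any unrestricted 1:1 scheme and is not evidence that any flip would be switched.

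**The case against.** The strongest objections concern allocation. A fair coin flipped after screening cannot be predicted, so it needs no concealed sequence. The source documents that section 9.2 says are included are not in the text available here, and they could hold an assignment field. These objections stand. They reduce this part of the point to a record that the visible passages do not describe, and a log cures that.

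A reader might go further and infer that flips would be repeated or overridden, or that the trial could not demonstrate its allocation at all. The documents support neither inference: nothing in them suggests misuse, and the forms cannot be seen. A reader might also take the mismatch at 8.4 as a sign that masking was planned and then dropped. Other contents entries also disagree with the body (8.3 against 8.2, and 9.3 against 9.4), so the mismatch is editorial and weak evidence either way.

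On masking, it can be said that this is a single-center pilot, that whoever gives the injection cannot be masked, and that one primary endpoint is instrument-read. All of that is fair. It limits the reach of the concern but leaves staining and satisfaction unprotected. The size of the lean is assumed, with no anchor in the documents.

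**Conclusion.** The concern holds for masking: in the visible text, neither the patient nor the staining grader is kept unaware of the allocation, so a co-primary and the secondary endpoint are open to expectation bias. Osmolarity is much less affected.

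Under the stated assumptions, the false-positive rate on an exposed score would rise from 5% to about 9-34% with 20 v 20 patients, and to about 14-59% (ρ = 0) or 23-87% (ρ = 0.5) with 40 fellow-eye pairs. These figures show sensitivity to an assumed lean. They do not predict that a lean will occur.

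For allocation, the supported conclusion is only that no record of the flip is described. The documents do not support a finding that the coin is an invalid method or that it must be replaced. The change is worth making because it is cheap, but the gap does not make the trial uninterpretable.

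**What to change.** Amend sections 3.1, 5.3 and 8.4 as follows.

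1. **Patients.** Do not tell patients their allocation (group, or which eye) until the Day 21 assessments of the last study eye are recorded, and say so at consent. This is practical because both groups use the same drops and DEXYCU is given during surgery. Use 8.4 to state how early disclosure is handled, which also reconciles it with the contents entry.
2. **Grader.** If an existing qualified team member is available, have that person grade staining without being told the allocation. If not, state that staining is graded unmasked and rest the less bias-prone conclusion on osmolarity.
3. **Flip.** Keep the coin. Enter each result once in a dated, witnessed log before first-eye surgery, match it to the kit number where DEXYCU is assigned, and state whether the flip assigns the patient or the eye. A concealed list is optional. If the assignment is already recorded on the source forms, cite that form instead.

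The cost is protocol and consent wording and a little more record-keeping, with no added visits. Section 9.1 limits access to information to the principal investigator, so it needs a line to cover a separate grader or a witness. The documents do not show that a second qualified grader exists, so item 2 is conditional. If staining stays unmasked, the price is a more guarded reading of that endpoint.

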3.2 Primary/Secondary Endpoints

Primary endpoints:

- 1) Tear film Osmolarity as measured on Tear Lab system
- 2) Corneal Staining (Oxford grading scale 0-15)

Secondary endpoint:

- 3) Satisfaction questionnaire – How satisfied are you with your surgery? (Graded 0-4)

4 Subject Selection and Withdrawal

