7.2 Statistical Methods

An ANOVA analysis will be performed to compare the dry eye testing data between the DEXYCU group and the standard regimen group.

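### Two primary endpoints have no named visit, summary measure, alpha or rule for a positive result, so the false-positive rate is undefined and can exceed 5%

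*Combined protocol and SAP*

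**What the plan says.** Section 3.2 lists the primary endpoints as "Tear film Osmolarity as measured on Tear Lab system" and "Corneal Staining (Oxford grading scale 0-15" on the scale's own range. No visit, summary measure or threshold follows.

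The whole of section 7.2 reads: "An ANOVA analysis will be performed to compare the dry eye testing data between the DEXYCU group and the standard regimen group". Alpha, sidedness, covariates, the form of ANOVA and the criterion for success are not stated there or anywhere else, and nothing is blacked out at these points.

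The timing differs by section. The Study Summary says "patients will have dry eye testing at 1 week and 3 weeks after surgery", and section 3.1 agrees: "Patients undergoing cataract surgery will have dry eye testing prior to surgery, 1 week after surgery, and 3 weeks after surgery". Section 6 lists a Day 1 visit as well and says "At all visits, visual acuity, eye pressure measurements, tear film osmolarity, and corneal staining will be measured and recorded".

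The unit of comparison is also unclear. Under sections 3.1, 5.3 and 8.4 patients "will be randomized to the DEXYCU group (standard postoperative cataract regimen + intraoperative DEXYCU) in one eye or the STANDARD group", which mixes patient and eye. Section 5.3 adds "Patients who are randomly assigned to the DEXYCU group will receive a sequentially numbered drug kit", which sounds like allocation by patient.

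Section 7.1 calls the study a single-center pilot and sets 40 patients by feasibility.

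**The concern.** With two primary endpoints and at least two scheduled post-operative visits, several analyses fit the text equally well: one comparison per endpoint, or a separate test of each endpoint at each visit. Each can be done on the post-operative value or on change from screening. The plan does not say whether one significant endpoint is enough or both are needed.

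A reader of the results could not tell a planned finding from one selected after the data were seen. If either endpoint counts and each is tested at 5%, the overall error rate is above 5% even with a single visit, and it rises with each visit left open.

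**Working it through.** **Inputs from the documents.** Two primary endpoints (3.2). Two scheduled post-operative dry eye tests, at weeks 1 and 3 (Study Summary, 3.1). 40 patients (7.1). Coin-flip allocation (3.1, 5.3, 8.4), hence 20 per group only in expectation. Screening values of both measures are collected (4.3, 6).

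**Assumptions, none stated in the documents.** Two-sided 5% per test, parallel groups of 20, normal data, correlation 0.3-0.9 between visits and 0-0.8 between endpoints. The sample size of 40 cannot be reproduced, because no effect size, SD, alpha or power is given.

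**Step 1: independent-test limit.** Chance of at least one false positive = 1 − 0.95^k.
- k = 2 (one comparison per endpoint): 1 − 0.9025 = 9.75%.
- k = 4 (two endpoints, two visits): 1 − 0.8145 = 18.5%.

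**Step 2: correlated tests.** Simulation of 40,000 null trials per setting, t tests, any one significant result counting:

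| Correlation between visits / endpoints | 2 tests | 4 tests |
|---|---|---|
| 0.3 / 0 | 9.6% | 17.9% |
| 0.5 / 0.3 | 9.5% | 16.8% |
| 0.8 / 0.5 | 9.1% | 14.1% |
| 0.9 / 0.5 | 9.2% | 12.6% |
| 0.9 / 0.8 | 7.8% | 11.0% |

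So about 8-10% and 11-18%.

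**Step 3: direction.** Those rates count results in either direction. Counting only results that favour DEXYCU gives 4.1-5.1% (2 tests) and 5.4-9.3% (4 tests). The matching nominal rate for one two-sided 5% test is 2.5%.

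**Step 4: fellow eyes.** With one treated and one control eye per patient and a paired test, the rates are 7.7-9.6% (2 tests) and 11.2-17.0% (4 tests). If the ANOVA ignores the pairing and the between-eye correlation is 0.5, each test has a true level of about 0.7% and the totals fall to 1.1-1.3% and 1.6-2.4%.

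**Step 5: both endpoints required.** At one named visit the error is 0.2-2.2% if neither endpoint responds and at most 5% if one does. If the visit is free (weeks 1 and 3) and one endpoint truly responds, the error depends on the size of that effect:
- 0.64 SD (about 50% power): at most about 5%.
- 0.909 SD (80% power): about 4-8%.
- Very large effect, the limiting case: 7.0-9.5%.

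**Step 6: what the fix gains and costs** (80% power, noncentral t).
- Unadjusted 20/20: 0.91 SD at alpha 0.05.
- Adjusted for screening at an assumed correlation of 0.5: 0.909 × √(1 − 0.5²) = 0.909 × 0.866 = 0.79 SD.
- Strictest Holm step (alpha 0.025), unadjusted: 1.009 SD; 1.009 / 0.909 = 1.11, about 11% larger. Adjusted: 0.87 SD.
- Both required, each endpoint at 80% power: 0.80² = 64% if independent, up to 73% at an endpoint correlation of 0.8.

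**The case against.** The strongest reply is the pilot label in section 7.1: a feasibility-sized study need not carry a confirmatory error framework. This stands in part. It makes the stakes moderate and makes a descriptive analysis a legitimate remedy. It does not remove the gap, because the document also calls the study a randomized controlled trial, names primary endpoints, plans a between-group test and nowhere calls the analysis descriptive.

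A second reply is that the ANOVA might be one repeated-measures model over weeks 1 and 3, giving one test per endpoint. That would be sound, but it is not specified, and the two-endpoint question (8-10%) would remain.

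Third, the rates rest on assumptions. This stands: they illustrate and do not bound. Staining is a bounded grade, so normality is a simplification.

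A reader might also infer stronger forms that the documents do not support:
- *Six comparisons, with Day 1 counted, at about 13-25%.* Section 7.2 analyses the dry eye testing data, and the Study Summary and 3.1 place post-operative dry eye testing at weeks 1 and 3. Day 1 enters only through the list of measurements in section 6.
- *Higher rates from pooling both eyes as independent.* No section says this would be done.
- *That requiring both endpoints still always gives 7-10%.* That is the large-effect ceiling only.
- *That the error is inflated on every reading.* Ignoring fellow-eye pairing makes the test conservative.

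**Conclusion.** The omission is established from the text alone: no primary visit, summary measure, alpha or success rule is given for two primary endpoints. A planned result therefore cannot be told from a selected one, and that conclusion needs no numerical assumption.

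The size is conditional. With valid two-sided 5% tests and either endpoint counting, the false-positive chance is about 8-10% for one comparison per endpoint and 11-18% for separate tests at weeks 1 and 3, or about half that for results favouring DEXYCU. These figures rest on the parallel 20/20 layout, normality and the assumed correlations. Other readings of the same text fall below 5%. The plan does not fix its own error rate, and nothing in it shows an intention to select. The sponsor should correct this; the pilot status keeps the consequence moderate.

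**What to change.** Before any data are seen:

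1. In 3.2, name one primary comparison per endpoint: either a single named visit, or one pre-specified repeated-measures comparison over weeks 1 and 3. The sponsor chooses and gives the reason. All other results become secondary.
2. In 7.2, replace the plain ANOVA with a group comparison adjusted for the screening value. This also settles the choice between post-operative value and change. If fellow eyes are compared, use an analysis that respects the pairing.
3. State a two-sided 5% family level with one named rule: Holm, a fixed order (naming the first endpoint), or both endpoints required. Alternatively, state that this pilot is descriptive and report estimates with confidence intervals and no claim of success.
4. Reconcile the dry eye testing visits in the Study Summary, 3.1 and 6, and the patient-or-eye wording in 3.1, 5.3 and 8.4.

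**Cost.** A few sentences, with no new visits or measurements. Results at other visits can no longer be called primary. Each rule has its own price: Holm raises the detectable difference at its strictest step, a fixed order tests the second endpoint only if the first succeeds, and requiring both lowers joint power to about 64-73% where each endpoint alone has 80%. The descriptive route gives up any claim of a positive trial. Adjustment for screening works the other way: at the assumed correlation of 0.5 it more than offsets the Holm penalty (0.87 against 0.91 SD unadjusted at 5%).

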4.1 Inclusion Criteria

- 1) Patients diagnosed with bilateral cataracts and scheduled to undergo bilateral cataract surgery
- 2) Must be able to understand and sign an informed consent from that has been approved by an Institutional Review Board
- 3) Patient is over the age of 18
- 4) Patient must agree to comply with visit schedule and other requirements of the study
- 5) Females who are not pregnant and are not lactating. Females who are post-menopausal or surgically sterilized.

If the answer to any of the inclusion criteria are NO, the subject is ineligible to continue study participation

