9.1 Confidentiality

A confidential study binder will be maintained and secured in a locked cabinet by the principal investigator.

All identifiable, sensitive information will be protected on a password protected, encrypted device.

What information is being collected?

Visit Date

Date of Surgery

Eye

Concomitant Medication

Ocular Symptoms (Graded 0-3)

 Foreign Body Sensation

 Tearing

 Photophobia

Visual Acuity

Intraocular Pressure

Tear Film Osmolarity

Corneal Staining

Patient satisfaction score

Will identifiers be removed? When?

Identifiers will be removed 3 months after study completion

How will the information be used?

The information will be used to determine if Dexycu treatment impacts dry eye parameters after cataract surgery

Will the information be sold to third parties?

No

Will the information be used for future research?

No

Who has access?

Only Principal Investigator

When will the information be destroyed?

12 months after study completion

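### The satisfaction item names no eye and the visits name no surgery, so in patients having both eyes operated on, attribution of the only secondary endpoint to DEXYCU or STANDARD is not assured

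*Combined protocol and SAP*

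**What the plan says.** - **Population.** Section 4.1 admits patients who are "scheduled to undergo bilateral cataract surgery", so two operations are expected for each.
- **Allocation.** Section 3.1 has patients "randomized to the DEXYCU group (standard postoperative cataract regimen + intraoperative DEXYCU) in one eye or the STANDARD group". Sections 3.1, 5.3 and 8.4 place one coin flip before the first eye's operation. None of them says how the other eye is treated or whether it is in the study.
- **Visit clock.** Section 3.1 gives participation as "3 weeks after cataract surgery", with testing at 1 and 3 weeks. It does not say whether this means the first operation, the second or each one. No interval between the operations is given.
- **Endpoint.** Section 3.2 lists one secondary endpoint, "How satisfied are you with your surgery", scored 0 to 4. Section 6 adds: "At days 7 and 21, patient satisfaction scores will be measured".
- **Recording.** Section 9.1 lists a "Patient satisfaction score" among the data items, and also lists eye and date of surgery. The binder in sections 5.4 and 9.2 has one tab each for Day 1, Day 7 and Day 21.
- **Analysis.** Section 7.2 plans an ANOVA of the dry eye test data between the two groups. It does not mention satisfaction.

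**The concern.** A patient who has had both eyes operated on and is asked about the surgery in general may answer for the first eye, the second, or both together. If the two eyes were treated differently, that answer carries both treatments in unknown proportion. An analysis term for eye order does not help, because it cannot divide one patient-level number between two eyes.

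The missing visit anchor adds to this. Without a named operation, Day 7 and Day 21 are not fixed to an eye and a date. That also touches the osmolarity and staining measurements, although those can at least be taken eye by eye.

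What is at stake is the interpretability of the only secondary endpoint. An answer collected without naming an eye cannot be assigned to one afterwards, so this has to be settled before data collection.

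**Working it through.** The plan's 40 patients cannot be reproduced. Section 7.1 sets that number on feasibility and gives no alpha, power, effect size or SD. The check therefore covers timing, attribution and what 40 patients could support.

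**1. Which answers follow both operations.** Let g be the gap in days between the operations (an assumption, since it is not stated), and suppose answers are taken at Days 7 and 21 after each. The second eye's answers always follow both operations. The first eye's Day 7 answer does so if g < 7, and its Day 21 answer if g < 21. The two 21-day windows overlap by max(0, 21 − g) days.

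| Gap g | Answers given after both operations | Overlap of windows |
|---|---|---|
| 3 days | all four | 21 − 3 = 18 days |
| 14 days | first-eye Day 21, both second-eye | 21 − 14 = 7 days |
| 21 days or more | both second-eye only | 0 days |

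**2. Fellow-eye reading (one DEXYCU eye, one STANDARD eye).** Let D and S be true satisfaction with each eye.
- One answer per visit that names no eye is a single number combining D and S. It has no partner to subtract, so there is no within-patient contrast.
- Suppose answers are linked to an eye, but a share w of each reflects the other eye. The difference is [(1 − w)D + wS] − [(1 − w)S + wD] = (1 − 2w)(D − S). The retained contrast is 0.8 at w = 0.1, 0.5 at w = 0.25 and 0 at w = 0.5.
- If only the second eye's answer is affected, the retained contrast is 1 − w. For example, D − [(1 − w)S + wD] = (1 − w)(D − S).

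**3. Patient-level reading.** The answer maps to the randomised arm. Assume the other eye is treated alike in both arms. Let p be the share of patients whose other eye is operated on before the visit, and w the weight they give it. The retained contrast is 1 − pw. The documents do not give p, so it runs from 0 to 1. At w = 0.25 the retained contrast lies between 1 and 0.75, and at w = 0.5 between 1 and 0.5. If both eyes of a patient received the arm's treatment, this dilution would not arise.

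**4. What 40 patients could detect** (assumed two-sided 5%, 80% power, no loss).
- 40 pairs, normal approximation: (1.960 + 0.842)/√40 = 0.443 SD of the paired difference. The paired t-test gives 0.454.
- 20 against 20 patients, normal approximation: 2.802 × √(2/20) = 0.886 SD of the score. A coin flip does not guarantee an equal split.

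These two figures are in different units. The SD of a paired difference is SD × √(2(1 − ρ)), which equals the SD of the score only at ρ = 0.5. On a five-level score, both are approximate.

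**The case against.** The strongest reply is that much of the text reads as a parallel comparison of patients. Section 5.3 speaks of patients assigned to the DEXYCU group, section 5.1 describes a kit as one dose for one patient, and section 7.2 compares two groups. On that reading a patient-level answer belongs to an arm, and only dilution of unknown size remains. This stands, and it is why failure is claimed for the fellow-eye reading only. The phrase placing DEXYCU in one eye keeps that reading open.

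A reader might also infer three stronger things that the documents do not support:
- **That satisfaction is asked once per patient.** Section 6 has two time points and does not say whether they are per patient, per eye or per operation. The label and the single visit tabs suggest patient level. The eye field in section 9.1 leaves eye-specific recording possible. Section 9.2 says that copies of the source forms are attached. They are not in the text available here and may identify the eye.
- **That follow-up of the two eyes overlaps.** It does so only if the operations are less than 21 days apart, and no interval is stated.
- **That no usable comparison exists at all.** Even in a fellow-eye design, if the coin decides which eye receives DEXYCU, first-eye answers given before the second operation allow a randomised comparison between patients.

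Finally, satisfaction with surgery does not measure the signs and symptoms of dry eye named in section 2, and this is a 40-patient pilot. That limits the importance of the point but does not remove it.

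**Conclusion.** The concern holds in a limited form. The protocol leaves undefined the unit of comparison, the operation that anchors the visits, and the eye to which the satisfaction answer refers. Attribution to DEXYCU or STANDARD is therefore not assured.

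Attribution fails within patients if the fellow eye is the control and the item is used as worded. Under patient-level randomisation the comparison survives, with a retained contrast of 1 − pw. Both p and w are unknown, and the form of the loss assumes the other eye is treated alike in both arms. The conclusion that the item cannot be attributed under any reading goes beyond the text.

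The change should be made because it is nearly free and cannot be made after the answers are collected. It is not a threat to the trial as a whole, since it bears mainly on a secondary endpoint.

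**What to change.** 1. State in sections 3.1, 5.3 and 7.2 whether the unit of comparison is the eye or the patient, and what role the other eye has.
2. In sections 3.1 and 6, count Days 1, 7 and 21 from each study eye's own surgery date. Section 9.1 already lists eye and surgery date as collected.
3. Reword the item in section 3.2 to ask about the surgery on the named study eye (right or left), with one score per study eye.
4. Record at each visit whether the other eye has been operated on.
5. State the satisfaction analysis in section 7.2, which now covers only the dry eye tests.

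Do not plan a paired analysis that drops every measurement taken after the other eye's operation. With sequential surgery in a fellow-eye design, that removes all second-eye outcomes and so every pair. If such an analysis is wanted, limit it to a supportive between-patient comparison of first-eye outcomes recorded before the second operation.

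The cost is one reworded question, one yes/no field and a few sentences of text. Some patients may find it hard to rate the eyes separately. No change to surgical scheduling is proposed.
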